### 4.5.2 Perioperative/inpatient data collection

During the inpatient phase of the participant's medical treatment, all data will be recorded on the "inpatient case report form" (CRF02).

To evaluate the presurgical dental occlusion (if occluding teeth present), a bite registration will be taken whilst the patient participant is anaesthetised. These will be obtained using a viscoelastic silicone impression material.

At surgery, overall time from knife to skin, to transferring the patient participant off the operating table will be recorded. Furthermore the timings of specific landmarks of reconstructive components of surgery will be recorded:

- Times at which mandibular osteotomies are first started (when mandibular cutting guides first touches mandible) and completed (when mandibular cutting guides removed)

- Time of knife-to-skin for flap harvest
- Time of flap detachment
- Time of completing fixation of the plate in its final resting position (i.e. when completion of fixation to the residual mandible)
- Time of completing arterial anastomosis

To evaluate the impact of cutting guides on the fit of the bony flap, the surgeon will be asked to record the number of subsequent adjustments needed to the mandibular/fibular osteotomies, drill holes and/or the plate itself.

To further evaluate the efficiency of either surgical technique (and any potential 'learning curve' effect), the surgeon and scrub nurse will be asked to provide a 5-point Likert scale rating for the following criteria at the end of the operation:

- Ease of use
- Confidence in performing the technique
- Immediate satisfaction with reconstructive component of surgery

In the immediate postoperative (inpatient) phase of recovery, dates of stay in the intensive care unit (ITU), high dependency unit (HDU) and/or the inpatient ward will be recorded, along with a final discharge date. During this period, any postoperative complications are to be recorded if/as they occur.

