## 3.2 Secondary outcomes

Secondarily, the study aims to compare treatment pathways A and B for:

2. The duration of surgery (in particular individual components of the surgery such as flap warm ischaemia time, duration of osteotomies and plate fixation procedures.

3. The operators' perceptions of the overall intraoperative usability, confidence with the technique and immediate satisfaction of the surgical result.
4. The need to make minor adjustments to either the plate, osteotomy or screw holes in order to fit the plate during surgery.
5. Incidence of postoperative complications (as recorded during inpatient stay as well as at 6 weeks, 6 months and 1 year outpatient follow up visits), for example:
  - a. Localised infection
  - b. Plate extrusion/exposure
  - c. Length of hospital stay (including duration of intensive care / high-dependency / ward requirements)
  - d. Mal / non / delayed-union of the bony components of the mandibular reconstruction (from objective analysis of clinically routine postoperative CT scan imaging)
  - e. Plate fractures/failures
6. Medium-term (up to 1 year) functional outcomes, for example:
  - a. Feasibility of dental implant rehabilitation (specifically in the technical context of clinical and/or radiological perspective of bone quality and anatomy as well as in the holistic context of the patient's suitability overall, in order to determine the importance of reconstructed bony anatomy in the decision processes and planning of dental rehabilitation)
  - b. Objective evaluation of changes in dental occlusion (with the aid of dental model analysis).
  - c. Objective assessment of changes in facial aesthetics (facial symmetry based upon baseline and postoperative 3D photography (stereophotogrammetry).
7. Patient-perceived quality of life:
  - a. using a validated quality of life assessment tools:
    - i. University of Washington Quality of Life Questionnaire v4
    - ii. Short-form Derriford appearance scale (DAS24)
    - iii. Liverpool oral rehabilitation questionnaire
  - b. by time to return to work / social status at 1 year (where applicable)
8. Economic implications (with economic analysis taking the above clinical and social outcomes into account).

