**Perioperative / inpatient data collection (CRF02 form).**

- Prior to commencing surgery, bite registration to be obtained (using viscoelastic silicone impression putty)
- At surgery, record of:
  - Times at which mandibular osteotomies are first started (cutting guides first placed onto mandible) and completed
  - Time of knife-to-skin for flap harvest
  - Time of flap detachment
  - Time of completing fixation of the plate (with flap) in its final resting position (i.e. when completion of fixation to the residual mandible)
  - Time of completing arterial anastomosis
- Record of need for any intraoperative adjustment to the plate, osteotomies and/or planned drill hole positions.
- Surgeon rating of usability, confidence of use, satisfaction with reconstructive procedure.
- Scrub nurse rating of usability, confidence of use, satisfaction with reconstructive procedure.
- Record of days-stayed on ITU / HDU and/or Ward, date of discharge.
- Record of all complications as inpatient (peri & post operative).

**6 weeks follow up** (CRF03 form).

- Physical assessment (BMI, oral hygiene status).
- University of Washington QoL questionnaire.
- Short-form Derriford appearance scale (DAS24).
- Liverpool oral rehabilitation questionnaire.
- Report on complications.
- 3D Photograph (Stereophotogrammetry) of the head and neck.
- Detailed social history (e.g. current occupation / employment)

**6 months follow up** (CRF04 form).

- Data recorded as per CRF03 form.
- Postoperative CT mandible scan (evaluation of actual vs. planned dimensions, quantitative evaluation of bony cortical union at osteotomy sites)

**1 year follow up** (CRF05 form).

- Data recorded as per CRF03 form.
- Dental assessment (including routine cone beam CT scan) and restorative dentist rating of technical and practical feasibility of prosthetic rehabilitation options

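### Osteotomy duration is to be compared between pathways, but only guided mandibular cutting is timed: fibular cuts and re-cuts after guide removal have no recorded time

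*Protocol*

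**What the plan says.** Protocol section 3.2, item 2, makes duration of surgery a secondary outcome, in particular "individual components of the surgery such as flap warm ischaemia time, duration of osteotomies and plate fixation procedures". The word osteotomies is not qualified by bone.

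Section 4.5.2 lists the landmarks to be timed. The osteotomy entry reads "Times at which mandibular osteotomies are first started (when mandibular cutting guides first touches mandible) and completed (when mandibular cutting guides removed". Its end point is thus "completed (when mandibular cutting guides removed". The CRF02 box in Figure 1 (section 4.0) has the same entry with a looser end point: "Times at which mandibular osteotomies are first started (cutting guides first placed onto mandible) and completed". Neither place lists a start or a finish for the fibular osteotomies. The flap-related landmarks are "Time of knife-to-skin for flap harvest", "Time of flap detachment", the end of plate fixation and the end of the arterial anastomosis. Overall operating time is also recorded.

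Section 4.5.2 then asks the surgeon for the "number of subsequent adjustments needed to the mandibular/fibular osteotomies, drill holes and/or the plate itself". This is a count, and it serves secondary outcome 4 in section 3.2. No time is attached to it.

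**The concern.** Section 4.1 requires a planned fibular free flap in every participant. Section 2.2 credits cutting guides with more accurate bone cuts in this operation, and section 2.4 names alignment of osteotomies as part of the rationale for the printed approach. The fibular cuts are therefore central to the comparison, yet they have no clock of their own.

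On the mandible, the clock stops when the guide comes off. Any correction made after that is outside the interval. Two pathways could then show the same recorded osteotomy time although one of them needed more bone work to make the reconstruction fit.

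What is at stake is one named component of a secondary outcome. Times that nobody writes down in theatre cannot be reconstructed later, so this cannot be left to an analysis plan.

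**Working it through.** The protocol states no osteotomy duration, standard deviation, effect size or power for this outcome, so there is no figure to reproduce. The check is of the text, followed by an illustration on assumed values.

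**Step 1: what the outcome needs against what the landmarks give.**

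- *Mandibular osteotomy under the guide.* Start and end are both recorded (section 4.5.2), so this can be measured.
- *Mandibular re-cut after guide removal.* It is counted but not timed. If done before the plate is fixed, its minutes lie between guide removal and end of fixation, mixed with other steps. No start of fixation is listed that would narrow this down.
- *Fibular osteotomy.* Neither start nor end is recorded. The start of harvest is not the start of bone cutting, and detachment is not defined as its end. Fibular work done before fixation ends lies somewhere between harvest start and end of fixation. No subtraction of listed landmarks isolates it.
- *Fibular re-cut.* It is counted but not timed, as for the mandible.

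Only the first of these four parts can be measured on its own.

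**Step 2: are the two statements of the end point the same?** Section 4.5.2 ties completion to guide removal. Figure 1 says only that the osteotomies are completed. If a guide is put back for a further cut, section 4.5.2 does not say which removal counts, and under Figure 1 the last cut could be taken as the end. Two recorders could enter different times for the same case.

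**Step 3: illustration of size (all inputs assumed).** For the mandible:

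recorded time = full osteotomy time − minutes of re-cutting after guide removal

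Error in the between-pathway difference = (difference in re-cuts per patient) × (minutes per re-cut)

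- Re-cut in 4 of 10 patients against 1 of 10, 10 minutes each: (0.4 − 0.1) × 10 = 3 minutes per patient.
- Same frequencies, 5 minutes: 0.3 × 5 = 1.5. With 20 minutes: 0.3 × 20 = 6.
- Wider assumptions, a difference of 0.5 to 2 re-cuts per case at 5 to 15 minutes: 0.5 × 5 = 2.5 up to 2 × 15 = 30 minutes.
- Equal re-cut time in both pathways: 0.

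**Step 4: direction.** This term alone makes the pathway with more re-cutting look quicker than it was. A second term works the other way: the clock starts at first contact of guide and bone, so time lost seating a badly fitting guide is inside the interval and lengthens it. The documents do not say which term is larger. The missing fibular time has no known direction at all.

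**The case against.** A reader might infer that the measure favours the pathway whose guides fit worse. The documents do not support that. It would need worse fit to produce more or longer re-cuts after guide removal, and the excess to outweigh the seating time that the interval already captures. Neither is shown.

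The remaining case for the plan is fair in several respects:

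- Adjustments are a secondary outcome in their own right (item 4) and are counted for both bones, the drill holes and the plate. A quick guide that leaves poor cuts would show up there, and possibly in the surgeon and scrub nurse ratings.
- Re-cut and fibular time is not lost altogether. It stays in overall operating time and, when spent before fixation ends, in composite intervals that can be compared between pathways. For the same reason, the economic outcome is not shown to be damaged.
- Asking for the number of adjustments does not mean that any will occur. A re-cut made with the guide put back might also fall inside the interval.
- Osteotomy duration is given as an example component, in a pilot of at least 10 patients per pathway, and the primary outcome of dimensional accuracy does not depend on it.

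These points limit the consequence. They do not close the gap: osteotomy duration is named for comparison without limitation to the mandible, and the listed landmarks deliver only its guided mandibular part. CRF02 itself is not reproduced in the protocol. If it already holds fibular times, section 4.5.2 and Figure 1 need only be brought into line with it.

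**Conclusion.** The point holds as a mismatch between a named outcome and the data listed for it. The recorded interval is guided mandibular osteotomy time. It leaves out fibular osteotomies for every patient and any re-cut made after the guide is off, and the two descriptions of completion differ.

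It can understate osteotomy time in a pathway that needs more re-cuts, but a net bias in either direction is not established. The illustrative 3 minutes per patient (1.5 to 6, or 2.5 to 30 on the wider assumptions, and 0 if re-cut time is equal) rests wholly on assumed frequencies and durations. Without a standard deviation or a typical duration, none of these figures shows that the effect is material.

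The change is worth making because it is cheap and the data cannot be recovered later. The primary outcome, overall operating time and the adjustment count stand as planned.

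**What to change.** In section 4.5.2, Figure 1 and CRF02:

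1. Add a start and a finish time for the fibular osteotomies.
2. Record the minutes spent on any mandibular or fibular re-cut after guide removal, beside the existing count.
3. Use one definition of completion in section 4.5.2 and Figure 1, with the same end point for both bones, and say how a guide that is put back is handled.
4. In section 3.2, item 2, state that osteotomy duration is reported as three components: guided mandibular time, fibular time and re-cut time. If they are added, call the sum working time. The documents do not say whether work on the two bones overlaps, so the sum should not be presented as elapsed theatre time.

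If the fields are not added, rename the measure *guided mandibular osteotomy time* in section 3.2 and report it beside the adjustment count.

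The cost is a few more time entries by theatre staff on a form already completed during surgery. Only recording changes; treatment does not.

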#### 4.5.3 6 weeks follow up

This will include reporting of any complications since discharge from hospital, as well as repetition of some data collected in the baseline assessment, using the "6 weeks case report form" (CRF03). Specific data to be collected includes:

- Physical assessment (BMI, oral hygiene status, report on wound healing).
- University of Washington QoL questionnaire.
- Short-form Derriford appearance scale (DAS24).
- Liverpool oral rehabilitation questionnaire.
- Report on complications.
- Stereophotogrammetry (3D photography) of the head and neck.

#### 4.5.3 6 months follow up

The "6 months case report form" (CRF04) will be used to collect identical data to that collected at 6 weeks follow-up. This follow up point is selected as in the case of cancer surgery, it is a standard follow-up point for assessment of signs of early disease recurrence. For this reason, routine medical CT scanning to evaluate for disease recurrence is performed. A 3D render of DICOM data from this clinical scan can be used to dimensionally and volumetrically compare the actual bony reconstruction with the preoperative plan, evaluating overall accuracy and precision of the reconstructive technique used. Furthermore, CT assessment of bony union will be performed using a quantitative numerical rating score, adapted from Akashi et al.(Akashi et al., 2015)

#### 4.5.4 1 year follow up

The “1 year care report form” (CRF05) will be used to collect identical data to that collected at 6 weeks follow-up. Furthermore, in some cases routine clinical and radiographic (cone beam CT) dental assessment is performed 1 year postoperatively with a view to further dental rehabilitation (with dental implants in some patients). From this dental assessment, we would aim to evaluate the clinician’s opinion (using a 5 point Likert scale) of the patient participant’s overall suitability for dental rehabilitation (if not already in place) with a variety of possible prosthetic solutions:

- Simple dentures
- Bridge
- (Multiple) single tooth implants
- Implant retained bridge
- Implant retained dentures

Dental radiology (cone beam CT) if used as part of this routine dental assessment will also be analysed to further evaluate any bony (dimensional/volumetric/healing) changes that occur over time. Post-surgical dental occlusion would clinically routinely be evaluated with a bite registration. This can be compared to the pre-surgical bite registration to evaluate the impact of the reconstructive surgery on dental occlusion.

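### Section 4.5.4 rates only overall suitability for dental rehabilitation, although outcome 6a also needs a bone-based judgement and Figure 1 describes the same rating differently

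*Protocol*

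**What the plan says.** Three places in the protocol describe this outcome.

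- **Section 3.2, item 6a** sets the aim. Feasibility of dental implant rehabilitation is to be considered "specifically in the technical context of clinical and/or radiological perspective of bone quality and anatomy", and also in the wider context of the patient. The purpose follows: "in order to determine the importance of reconstructed bony anatomy in the decision processes and planning of dental rehabilitation".
- **Section 4.5.4** gives the instrument. The clinician's opinion is taken "using a 5 point Likert scale", and what is rated is the participant's "overall suitability for dental rehabilitation (if not already in place) with a variety of possible prosthetic solutions". Five solutions are listed: simple dentures, a bridge, and three that rest on implants.
- **Section 4.0, Figure 1**, in the box for the 1-year visit (CRF05), describes the item as a "restorative dentist rating of technical and practical feasibility of prosthetic rehabilitation options".

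Section 4.5.4 adds that "in some cases routine clinical and radiographic (cone beam CT) dental assessment is performed 1 year postoperatively", so not every participant will have a rating. It also provides for the bone to be looked at on cone beam CT, but only "if used as part of this routine dental assessment will also be analysed to further evaluate any bony (dimensional/volumetric/healing) changes that occur over time".

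**The concern.** Item 6a needs two things that can be told apart: what the bone would allow, and what the patient as a whole is suited to. The section that defines the measurement supplies only the second. A patient may be rated low because the bone is poor, or because of comorbidity, oral hygiene, earlier radiotherapy or a change in prognosis after surgery, and the score does not show which.

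This matters somewhat more because treatment is not randomised. The surgeon chooses the pathway in the usual clinical way, so the mix of patients may differ between A and B. A rating that takes in everything about the patient can carry such a difference into the comparison.

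It is also not a detail that an analysis plan can supply later. A judgement that was never asked for at the visit cannot be recovered at analysis.

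**Working it through.** No arithmetic applies. The protocol states no effect size, power or precision for this outcome. The check is to set the passages side by side.

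**1. Constructs in the aim.** Item 6a has two components, technical (bone quality and anatomy) and holistic (the patient overall), and one purpose, the weight of the reconstructed bone in planning.

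**2. Constructs in the instrument.** I read section 4.5.4 as asking for one rating per listed solution. That gives 5 ratings per assessed participant, all of the same construct, overall suitability. No technical or bone-based rating is named, and no reason for a low rating is requested. Component 1 of 6a therefore has no defined measurement in this section.

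**3. Constructs in Figure 1.** The figure names two aspects, technical and practical, for the same visit. It does not say whether they are two scores or one. Nor does its wording match section 4.5.4, since the practicality of a prosthesis is not obviously the same thing as the overall suitability of the patient.

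**4. What else could show the role of bone.**

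| Source | Where | Limit |
|---|---|---|
| Actual versus planned dimensions, and a bony union score, from CT at 6 months | 4.5.3 (6 months), Figure 1 | Measures geometry and healing, not whether bone drove the decision |
| Bony change on cone beam CT at 1 year | 4.5.4 | Only where the scan was part of the assessment |
| Comorbidity and performance scores, radiotherapy history, oral hygiene | 4.5.1; oral hygiene again at follow-up | Mostly baseline values |
| Contrast within a patient between implant-based (3) and other (2) solutions | 4.5.4 | General patient factors are partly shared, but the solutions also differ in other ways |

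Section 6.0 allows correlation and regression in general terms, so the ratings could be related to these measures.

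**5. How far that route goes.** The minimum is 10 participants per pathway, 20 in all, and those with a 1-year dental assessment may be fewer. Relating an ordinal rating to several bone measures and several patient factors in so few people gives an indirect and imprecise answer. A direct question to the clinician avoids that problem.

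**The case against.** The strongest case on the other side is that this is a mismatch of wording and not a gap in the data. Figure 1 does name a technical aspect. CRF05 is not shown and may already score it separately. Bone is measured on CT, most of the relevant patient factors are recorded, and five solutions are rated, so the ratings carry some information about bone. Overall suitability is itself part of 6a, and 6a does not literally prescribe two scores. The item is one of many secondary outcomes in an observational pilot, and it touches neither the primary outcome nor safety.

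Most of this stands, and it limits the point. A reader might infer three stronger things that the documents do not support:

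- *That the role of bone cannot be determined at all.* The CT measures and recorded patient factors leave an indirect route, and the form itself may separate the two aspects.
- *That the plate and guides can affect this outcome only through bone, so that pathways A and B should be compared on a bone-only rating.* Section 3.2 itself lists infection, plate exposure, plate failure and changed occlusion as outcomes to compare between pathways. Any of these could plausibly affect suitability for rehabilitation. A bone-only comparison would also drop the holistic half of 6a.
- *That a bias of a given number of scale points follows.* The protocol gives no figure for how many patients would be rated low for reasons other than bone. If such patients were equally common in both pathways, with equal effect on the ratings, they would produce no mean difference.

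What the objection does not remove is that section 4.5.4 and Figure 1 describe one rating in two ways, and that the section defining the instrument leaves out the component on which the purpose of 6a depends.

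**Conclusion.** The point holds as a minor one. Section 4.5.4, as written, measures the holistic side of outcome 6a and not the technical side. Figure 1 describes the same item in different terms and does not settle whether the aspects are scored separately. If section 4.5.4 is followed, the weight of the reconstructed bone can be inferred only indirectly, and weakly at about 10 participants per pathway with the assessment done in some of them.

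No numerical size can be given from the documents. The conclusion rests on two assumptions: that section 4.5.4 intends one rating for each of the five solutions, and that CRF05 follows section 4.5.4. If CRF05 already takes separate ratings, only the wording needs correcting.

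**What to change.** In section 4.5.4 and CRF05, have the same clinician, at the same assessment, give two 5-point ratings for each prosthetic option:

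1. technical feasibility, judged on bone quality and anatomy;
2. overall suitability of the patient.

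Record the main reason or reasons for any low overall rating. Report both ratings by pathway, and use rating 1 together with the recorded reasons to describe how far bone bears on the decision. Do not use the simple difference between the two ratings for this. When both are low the difference is zero, whether or not factors other than bone would also have ruled the patient out.

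Bring the wording of section 3.2 (item 6a), Figure 1 and section 4.5.4 into line.

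The cost is five further ratings per assessed participant (10 instead of 5) and a short reason field, about a minute of the clinician's time. No extra visit, imaging or assessor is needed, and care does not change. The change has to be made before the 1-year assessments, because the judgement is made at the visit.
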